#### **7.1.4.1 Withdrawal of consent**

Patients may voluntarily withdraw consent to participate in the study for any reason at any time. Withdrawal of consent occurs only when a patient does not want to participate in the study any longer, and does not want any further visits or assessments, and does not want any further study related contact.

Novartis will continue to retain and use all research results that have already been collected for the study evaluation. All biological samples that have already been collected may be retained and analyzed at a later date (or as required by local regulations).

If a patient withdraws consent, the investigator should make a reasonable effort (e.g. telephone, e-mail, letter) to understand the primary reason for this decision and record this information.

Everolimus must be discontinued and no further assessments conducted.

Further attempts to contact the patient are not allowed unless safety findings require communication or follow up.

Patients may be withdrawn from the study if any of the following occur:

- Death
- Lost to follow-up
- Staying in the study would be harmful
- Patient/guardian decision
- Physician decision
- Non-compliance to protocol requirements
- Protocol deviation
- Pregnancy
- Study terminated by sponsor
- Unsatisfactory therapeutic effect

#### **7.1.4.2 Replacement policy**

Not applicable.

### **7.1.5 Follow up for safety evaluations**

All patients must be followed up for safety evaluations for 30 days after the last dose of everolimus. At the end of this period, the investigator should contact the patient to inquire about any AE observed during this period. This could be done via a phone contact. Following this there are **no** further follow-up study visits.

### **7.1.6 Lost to follow-up**

For patients whose status is unclear because they fail to appear for study visits without stating an intention to withdraw consent, the investigator should show "due diligence" by contacting the patient, family or family physician as agreed in the informed consent and by documenting in the source documents steps taken to contact the patient, e.g. dates of telephone calls, registered letters, etc. A patient should not be considered lost to follow-up until due diligence has been completed. Patients lost to follow up should be recorded as such on the appropriate Disposition CRF.

## **7.2 Assessment types**

### **7.2.1 Efficacy assessments**

Not applicable.

### **7.2.2 Safety and tolerability assessments**

Safety will be monitored by collecting AEs throughout the study on a continuous basis. See [Section 8](#).

Women of child-bearing potential must complete the following pregnancy tests:

- Baseline/Enrollment - serum pregnancy test done locally
- Every 4 weeks during treatment - urine pregnancy test can be performed at patient's home.
- End of Treatment visit - serum pregnancy test done locally

Women of child-bearing potential who administer urine pregnancy testing at home should complete a simple diary with the dates and the outcome of the urine pregnancy test while on study treatment. In case of a positive pregnancy test, the instructions in [Section 8.4](#) should be followed.

### **7.2.3 Pharmacokinetics**

Not applicable.

### **7.2.4 Biomarkers**

Not applicable.

### **7.2.5 Resource utilization**

Not applicable.

## 7.2.6 Patient reported outcomes

Not applicable.

# 8 Safety monitoring and reporting

## 8.1 Adverse events

### 8.1.1 Definitions and reporting

An AE is defined as the appearance of (or worsening of any pre-existing) undesirable sign(s), symptom(s), or medical condition(s) that occur after patient's signed informed consent has been obtained.

Abnormal laboratory values or test results occurring after informed consent constitute AEs only if they induce clinical signs or symptoms, are considered clinically significant, require therapy (e.g., hematologic abnormality that requires transfusion or hematological stem cell support), or require changes in study medication(s).

AEs that begin or worsen after informed consent should be recorded in the AEs eCRF. AE monitoring should be continued for at least 30 days after the last dose of everolimus. AEs (including lab abnormalities that constitute AEs) should be described using a diagnosis whenever possible, rather than individual underlying signs and symptoms. When a clear diagnosis cannot be identified, each sign or symptom should be reported as a separate AE.

AEs will be assessed according to the Common Terminology Criteria for Adverse Event (CTCAE) version 4.03.

If CTCAE grading does not exist for an AE, the severity of mild, moderate, severe, and life-threatening, corresponding to Grades 1 - 4, will be used. CTCAE Grade 5 (death) will not be used in this study; rather, information about deaths will be collected in the End of Treatment eCRF page.

The occurrence of AEs should be sought by non-directive questioning of the patient during the screening process after signing informed consent and at each visit during the study. AEs also may be detected when they are volunteered by the patient during the screening process or between visits, or through physical examination, laboratory test, or other assessments. As far as possible, each AE should be evaluated to determine:

1. The severity grade (CTCAE Grade 1-4)
2. Its duration (Start and end dates or Ongoing at End of Study)
3. Its relationship to the study treatment (Reasonable possibility that AE is related: No, Yes)
4. Action taken with respect to study or investigational treatment (none, dose adjusted/ temporarily interrupted, permanently discontinued, concomitant medication taken, non-drug therapy given, hospitalization)
5. Whether it is serious, where a SAE is defined as in [Section 8.2.1](#)

All AEs should be treated appropriately. If a concomitant medication or non-drug therapy is given, this action should be recorded on the AE eCRF.

Once an AE is detected, it should be followed until its resolution or until it is judged to be permanent, and assessment should be made at each visit (or more frequently, if necessary) of any changes in severity, the suspected relationship to the study treatment, the interventions required to treat it.

Progression of malignancy (including fatal outcomes), if documented by use of appropriate method [for example, as per Response evaluation Criteria in Solid Tumors (RECIST) criteria for solid tumors or as per Cheson's guidelines for hematological malignancies], should not be reported as a SAE.

AEs separate from the progression of malignancy (example, deep vein thrombosis at the time of progression or hemoptysis concurrent with finding of disease progression) will be reported as per usual guidelines used for such events with proper attribution regarding relatedness to the drug.

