## **8.2      Serious adverse events**

### **8.2.1    Definitions**

Serious adverse event (SAE) is defined as one of the following:

- Is fatal or life-threatening
- Results in persistent or significant disability/incapacity
- Constitutes a congenital anomaly/birth defect
- Is medically significant, i.e., defined as an event that jeopardizes the patient or may require medical or surgical intervention to prevent one of the outcomes listed above
- Requires inpatient hospitalization or prolongation of existing hospitalization
- Note that hospitalizations for the following reasons should not be reported as SAEs:
  - Routine treatment or monitoring of the studied indication, not associated with any deterioration in condition
  - Elective or pre-planned treatment for a pre-existing condition that is unrelated to the indication under study and has not worsened since signing the informed consent
  - Social reasons and respite care in the absence of any deterioration in the patient's general condition
- Note that treatment on an emergency outpatient basis that does not result in hospital admission and involves an event not fulfilling any of the definitions of a SAE given above is not a SAE

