### **10.4.2 Adverse events (AEs)**

Summary tables for AEs have to include only AEs that started or worsened during the on-treatment period, the **treatment-emergent** AEs. However, all safety data (including those from the post-treatment periods) will be listed and those collected during the post-treatment period are to be flagged.

The incidence of AEs (new or worsening from baseline) will be summarized by system organ class and preferred term, severity (based on CTCAE grades), type of AE and relation to study treatment.

Deaths reportable as SAEs and non-fatal serious AEs will be listed by patient.

Specific safety event categories will be considered. Such categories consist of one or more well-defined safety events which are similar in nature and for which there is a specific clinical interest in connection with the study treatment(s).

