1.2.1 Adverse events (AEs)

Summary tables for AEs have to include only AEs that started or worsened during the on-treatment period, the **treatment-emergent** AEs. However, all safety data (including those from the post-treatment periods) will be listed and those collected during the post-treatment period are to be flagged.

The incidence of all treatment-emergent AEs (number and percentage) will be summarized by system organ class (SOC), preferred term, and maximum severity, relation to study treatment.

Deaths reportable as SAEs and non-fatal serious AEs will be listed by patient.

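### The only planned AE summary table merges fatal treatment-emergent AEs with survived events of the same grade, and no planned summary gives fatal-AE incidence by term or relation to everolimus

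*Protocol*

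**What the plan says.** Protocol section 8.1.1 grades AEs by CTCAE version 4.03 but states that "CTCAE Grade 5 (death) will not be used in this study". The same sentence gives the alternative: "information about deaths will be collected in the End of Treatment eCRF page". The section then lists five things to determine for each AE as far as possible. Severity is "The severity grade (CTCAE Grade 1-4"). Duration is "Its duration (Start and end dates or Ongoing at End of Study"). The others are relationship to treatment, action taken and seriousness. Outcome is not listed.

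SAP section 1.2.1 defines one AE summary, the number and percentage of patients with treatment-emergent AEs, broken down "by system organ class (SOC), preferred term, and maximum severity, relation to study treatment". Protocol section 10.4.2 describes much the same summary and adds an undefined breakdown by type of AE.

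Both documents also plan a listing: "Deaths reportable as SAEs and non-fatal serious AEs will be listed by patient". SAP section 1.1.2 summarises the primary reason for end of treatment. Protocol Table 3-1 gives a single endpoint, the frequency and nature of AEs.

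**The concern.** In a table by maximum severity, readers look to the top category for the worst outcomes. Here the top category is Grade 4, and nothing in the table shows which of those patients died. A fatal pneumonitis and one from which the patient recovered count alike if both were Grade 4, and a fatal event graded 3 appears lower still.

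At stake is the description of the study's only endpoint. The trial has no comparator, no efficacy assessment and no secondary objective, so the AE summary carries most of its result. Whether an event was fatal is part of its nature. A reader who wants the share of patients with a fatal AE for a given term, or the share judged related to everolimus, finds no planned table that gives it.

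**Working it through.** The plan gives no figure to reproduce, and no sample size, rate or test enters the argument. The check follows a fatal treatment-emergent AE through the records and outputs that the documents describe.

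1. **Severity (protocol 8.1.1).** Grades 1 to 4 are allowed, so the event takes Grade 4 or lower.
2. **Other listed AE items (protocol 8.1.1).** Duration allows dates or ongoing status. Relationship and action taken do not state an outcome. Seriousness is given as "Whether it is serious, where a SAE is defined as in" section 8.2.1, where one criterion reads "Is fatal or life-threatening". A yes on seriousness therefore does not distinguish a death from a life-threatening event that was survived.
3. **The summary table (SAP 1.2.1).** Its classifiers are system organ class, preferred term, maximum severity and relation. By step 1, maximum severity cannot mark the event as fatal, and the other three do not. The event shares a cell with survived events of the same term and grade.
4. **Other outputs that carry deaths.**

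| Output | What it shows | What it does not show |
|---|---|---|
| By-patient listing (protocol 10.4.2, SAP 1.2.1) | Deaths reportable as SAEs, apart from non-fatal SAEs | Number and percentage by term or relation |
| Reason for end of treatment (SAP 1.1.2) | Counts by primary reason | AE term, or relation of that AE |
| Breakdown by type of AE; specific safety event categories (protocol 10.4.2) | Content not defined | Neither is carried into the SAP, so neither can be counted on to hold a fatal category |

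5. **Illustration with assumed counts.** Suppose 4 patients have Grade 4 as their worst grade for one term. The number who died, d, can be 0, 1, 2, 3 or 4, so the fatal share of that cell runs from 0/4 = 0% to 4/4 = 100%. The table entry is 4 patients at Grade 4 in all five cases. The figure 4 is not from the documents.

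6. **Scope.** Summary tables cover only AEs that started or worsened from the first dose to 30 days after the last dose. Later AEs are listed and flagged, so the point concerns treatment-emergent AEs only. Under protocol 8.1.1, documented progression of malignancy, including fatal progression, is not reported as an SAE, so such deaths fall outside the listing by design.

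7. **Timing.** Protocol 7.1.4 schedules the End of Treatment visit as soon as possible after stopping, and 7.1.5 allows the 30-day safety contact by telephone. The text does not say how a death between the two reaches the End of Treatment page. If it is an SAE it must be reported under 8.2.2, so it should be on an SAE form. A link from that record to the AE term used in the table is not described.

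**The case against.** The strongest reply is that this is a deliberate convention. Severity and death are recorded separately, a source for deaths is named, and the planned listing already divides deaths from non-fatal SAEs. Counts by system organ class and preferred term are unaffected. The study is descriptive, and no test or decision depends on the Grade 4 cell. In a small study, the listing can be read beside the table.

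Most of this stands. It makes the gap one of presentation in the summary, not of lost data. It does not close the gap: a listing gives no incidence by term or relation and leaves the severity table unchanged.

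Three stronger readings are tempting, and the documents do not support them.

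- A reader might infer that the table is wrong, or that every fatal AE is misplaced by a grade. That compares it with a five-grade scale that the protocol says it does not use. On its own scale the events are placed as defined; the limitation is that fatal and survived events are merged.
- A reader might infer that the database cannot identify a fatal AE. The five items in 8.1.1 are what the investigator should try to determine, not an eCRF specification, and neither the eCRF nor the SAE form is among the documents. A listing that separates deaths from non-fatal SAEs presupposes that the distinction is recorded.
- A reader might infer that deaths go unreported. The listing and the End of Treatment page answer that for deaths reportable as SAEs.

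**Conclusion.** The point holds for the summary table and for fatal treatment-emergent AEs. As planned, the table cannot distinguish them from survived events of the same grade, and no other planned summary gives the number and percentage of patients with a fatal AE by term and relation to everolimus.

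Its size is unknown, since the documents state neither the number of patients nor an expected rate of fatal AEs. If there are none, nothing in the report changes. If there are some, all of them are affected in the table and the severity profile looks more favourable than one that shows deaths. The conclusion rests on reading SAP section 1.2.1 as the full specification of AE summaries; output shells outside these documents could add a fatal-AE table. This is a worthwhile, inexpensive improvement to the reporting of the sole endpoint, not an error that invalidates the analysis.

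**What to change.** Keep the Grade 1 to 4 convention in protocol 8.1.1. In SAP section 1.2.1, do one of the following:

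- add fatal as a separate category above Grade 4 in the maximum-severity table, with each patient counted once per term in the highest category reached; or
- add a companion table giving the number and percentage of patients with a fatal treatment-emergent AE by system organ class, preferred term and relation to study treatment.

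State in the SAP that fatal AEs are identified from the SAE and death records already needed for the planned listing. Before database lock, confirm that each death from the first dose to 30 days after the last dose is linked to its causal AE term or, where the cause is documented progression, identified as such.

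The cost is one table category or one table, and a reconciliation that draws on records the listing already needs. No treatment rule changes. A new eCRF field would be needed only if the reconciliation shows that the link cannot be made from existing records. The drawback for the sponsor is a less favourable severity profile if fatal AEs occur, by an amount that the documents do not allow one to estimate.

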### **8.1.2     Laboratory test abnormalities**

#### **8.1.2.1    Definitions and reporting**

Laboratory abnormalities that constitute an AE in their own right (are considered clinically significant, induce clinical signs or symptoms, require concomitant therapy or require changes in study treatment), should be recorded on the AEs eCRF. Whenever possible, a diagnosis, rather than a symptom should be provided (e.g. anemia instead of low hemoglobin). Laboratory abnormalities that meet the criteria for AEs should be followed until they have returned to normal or an adequate explanation of the abnormality is found. When an abnormal laboratory or test result corresponds to a sign/symptom of an already reported AE, it is not necessary to separately record the lab/test result as an additional event.

Laboratory abnormalities, that do not meet the definition of an AE, should not be reported as AEs. A Grade 3 or 4 event (severe) as per CTCAE does not automatically indicate a SAE unless it meets the definition of serious as defined below and/or as per investigator's discretion. A dose hold or medication for the lab abnormality may be required by the protocol in which case the lab abnormality would still, by definition, be an AE and must be reported as such.

### **8.1.3     AEs of special interest**

The treating doctor should be aware of the important potential risks of everolimus as reported in the current IB. In addition, the treating doctor should report any events noted below as AEs which are being closely monitored by safety to rule out causality:

Refer to preclinical toxicity and or clinical data found in the current everolimus IB.

In addition to all serious AEs reported on a continuous basis throughout the study, the investigator should use the SAE form to report the following medically significant potential risks:

- Postnatal development toxicity
- Pregnant or breast-feeding women
- Intestinal obstruction /ileus
- Male infertility

- Pancreatitis
- Cholelithiasis
- Muscle-wasting/Muscle-loss

## **8.2      Serious adverse events**

### **8.2.1    Definitions**

Serious adverse event (SAE) is defined as one of the following:

- Is fatal or life-threatening
- Results in persistent or significant disability/incapacity
- Constitutes a congenital anomaly/birth defect
- Is medically significant, i.e., defined as an event that jeopardizes the patient or may require medical or surgical intervention to prevent one of the outcomes listed above
- Requires inpatient hospitalization or prolongation of existing hospitalization
- Note that hospitalizations for the following reasons should not be reported as SAEs:
  - Routine treatment or monitoring of the studied indication, not associated with any deterioration in condition
  - Elective or pre-planned treatment for a pre-existing condition that is unrelated to the indication under study and has not worsened since signing the informed consent
  - Social reasons and respite care in the absence of any deterioration in the patient's general condition
- Note that treatment on an emergency outpatient basis that does not result in hospital admission and involves an event not fulfilling any of the definitions of a SAE given above is not a SAE

### **8.2.2    Reporting**

To ensure patient safety, every SAE, regardless of suspected causality, occurring after the patient has provided informed consent and until at least 30 days after the patient has stopped study treatment must be reported to Novartis within 24 hours of learning of its occurrence.

Any SAEs experienced after this 30 days period should only be reported to Novartis if the investigator suspects a causal relationship to the study treatment. Recurrent episodes, complications, or progression of the initial SAE must be reported as follow-up to the original episode within 24 hours of the investigator receiving the follow-up information. A SAE occurring at a different time interval or otherwise considered completely unrelated to a previously reported one should be reported separately as a new event.

Information about all SAEs is collected and recorded on the SAE Report Form; all applicable sections of the form must be completed in order to provide a clinically thorough report. The investigator must assess and record the relationship of each SAE to each specific study treatment (if there is more than one study treatment), complete the SAE Report Form in Japanese, and send the completed, signed form by fax within 24 hours to the Novartis Drug Safety and Epidemiology (DS&E) department.

The telephone and telefax number of the contact persons in the local department of DS&E, specific to the site, are listed in the investigator folder provided to each site. The original copy of the SAE Report Form and the fax confirmation sheet must be kept with the CRF documentation at the study site.

Follow-up information is sent to the same contact(s) to whom the original SAE Report Form was sent, using a new SAE Report Form stating that this is a follow-up to the previously reported SAE and giving the date of the original report. Each re-occurrence, complication, or progression of the original event should be reported as a follow-up to that event regardless of when it occurs. The follow-up information should describe whether the event has resolved or continues, if and how it was treated, whether the blind was broken or not, and whether the patient continued or withdrew from study participation.

If the SAE is not previously documented in the current IB or Package Insert (new occurrence) and is thought to be related to the Novartis study treatment, a Novartis DS&E department associate may urgently require further information from the investigator for Health Authority reporting. Novartis may need to issue an Investigator Notification (IN), to inform all investigators involved in any study with the same drug that this SAE has been reported. Suspected Unexpected Serious Adverse Reactions (SUSARs) will be collected and reported to the competent authorities and relevant ethics committees in accordance with Directive 2001/20/EC or as per national regulatory requirements in participating countries.

